## CORPATH GRX NEURO STUDY SUMMARY

TITLE	An Evaluation of Effectiveness and Safety of the CorPath® GRX System in Endovascular Embolization Procedures of Cerebral Aneurysms
SHORT TITLE	CorPath GRX Neuro Study
DEVICE	
CorPath GRX System:
 
 
• Bedside Unit consists of the Extended Reach Arm, Robotic Drive and single-use Cassette.
 
• Interventional cock pit
 
• Control console
 

REGULATORY STATUS	The CorPath GRX System is CE Marked effective March 27, 2019 (CE 549879).
INDICATION FOR USE	
The CorPath GRX System is intended for use in the remote delivery and manipulation of devices during percutaneous coronary and vascular procedures, including the following commercial devices:
 
 
• Guidewires
 
• Rapid Exchange Catheters
 
• Guide Catheters
 
• Microcatheters
 
• Embolization Coils
 
• Coil Assist Stents
 

STUDY OBJECTIVE	The primary objective of this study is to evaluate the effectiveness and safety of robotic-assisted endovascular embolization procedures compared to objective performance criteria for traditional, manual operation based on the scientific literature.
STUDY DESIGN	This is a prospective, single-arm, international, multi- center, non-inferiority study to evaluate the effectiveness and safety of the CorPath GRX System for endovascular cerebral aneurysm embolization compared to historical controls. Subject selection requires a clinical indication for endovascular coil and/or stent-assist coiling embolization of cerebral aneurysms.
STUDY COORDINATING PRINCIPAL INVESTIGATOR	
[name]          Service de Neuroradiologie Interventionnelle          Hôpital de la Fondation Rothschild          [name]          F - 75940 Paris, France

## SAMPLE SIZE

Up to 120 subjects will be enrolled in order to achieve at least 108 subjects in the study; each site will try to recruit a maximum of 20 subjects. If a site has the possibility to enroll more than 20 subjects, a written authorization will be required from the sponsor, Corindus, Inc.

## INVESTIGATIONAL SITES

A maximum of up to 20 international sites may participate in this study. This will depend on each active site's recruitment rate and the possible travel restrictions due to the Covid-19 pandemic.

## STUDY DURATION/ FOLLOW-UP PERIOD

The recruitment phase is 18 months, follow-up is 180-days, and total study duration is 24 months. All subjects will be followed post-CorPath GRX endovascular embolization procedure through 180-days.

## SUBJECT POPULATION:

Subjects with a clinical indication for endovascular coil and/or stent-assisted coiling embolization of cerebral aneurysms.

## INCLUSION CRITERIA

Candidates will be included in the study only if all the following conditions are met:

1. Age  $\geq$  18 years.
2. At least one cerebral aneurysm (unruptured) with indication for endovascular treatment; dome to neck ratio  $>1.5$  or aneurysm neck width  $>4.0$  mm.
3. The Investigator deems the procedure appropriate for both manual or robotic-assisted endovascular treatment.
4. The conscious subject has been informed of the nature of the study, agrees to its provisions and has provided written informed consent.

## EXCLUSION CRITERIA

Candidates will be excluded from the study if any of the following conditions are present:

1. Failure / unwillingness of the subject to provide informed consent.
2. The Investigator determines that the subject or the neurovascular anatomy is not suitable for robotic-assisted endovascular treatment.
3. Women who are pregnant.
4. Persons under guardianship or curatorship.

Procedure Title: CorPath GRX Neuro Study Protocol	
Doc Number: 104-08660	
Revision: I	Page: 8 of 69

## ELIGIBILITY COMMITTEE

The Eligibility Committee will be responsible for the evaluation of CorPath GRX Neuro subjects for participation in the study. In advance of all study subject enrollment and treatment, the committee will use subject clinical history, Unruptured Intracranial Aneurysm Treatment Score (UIATS) data, the treatment plan, and at least 4 angiographic (DSA or CTA/MRA) images to approve for inclusion into the study or exclude and defer treatment of the cerebral aneurysm with the CorPath GRX Robotic system.

## PRIMARY EFFECTIVENESS ENDPOINT

The primary effectiveness endpoint will be defined as successful completion of the robotic-assisted endovascular procedure absent any unplanned conversion to manual for guidewire or microcatheter navigation, embolization coil(s) or intracranial stent(s) deployment, or an inability to navigate vessel anatomy.

## PRIMARY SAFETY END- POINT

The primary safety endpoint will be a composite of intra- and peri-procedural events, defined as vascular injury including intra-procedural aneurysm rupture caused by robotically controlled catheters, wires, or devices and thromboembolic events with neurological decline (NIHSS score change  $\geq 4$ ) within 24-hours post- procedure or hospital discharge, whichever occurs first.

## SECONDARY END-POINTS

### Clinical Outcome

Clinical outcome as measured by Modified Rankin Scale. This is assessed at the 90-Day Follow-Up ( $\pm 14$  days) and at the 180-Day Follow-Up ( $\pm 30$  days from the procedure date);

### Robotically Navigate Device to the Target Aneurysm

Defined as successful advancement of device to the target aneurysm robotically;

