#### 3.2 Primary Effectiveness Endpoint

The primary effectiveness endpoint will be defined as successful completion of the robotic-assisted endovascular procedure absent any unplanned conversion to manual for guidewire or microcatheter navigation, embolization coil(s) or intracranial stent(s) deployment, or an inability to navigate vessel anatomy.

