#### 3.4 Secondary Endpoints

Several secondary endpoints will be examined in this trial, including the following:

- 1. Clinical Outcome** - Clinical outcome as measured by Modified Rankin Scale. This is assessed at 90-Day Follow-Up ( $\pm 14$  days) and 180-Day Follow-Up ( $\pm 30$  days from the procedure date);
- 2. Robotically Navigate Device to the Target Aneurysm** - Defined as successful advancement of devices to the target aneurysm robotically;
- 3. Robotically Navigate Device *into* the Target Aneurysm** - Defined as successful navigation of device into the target aneurysm robotically;
- 4. Robotically Deploy Therapeutic Device *into* Target Aneurysm** - Defined as successful deployment of therapeutic device into the target aneurysm robotically;
- 5. Overall Procedure Time** - Defined as the time measured from the insertion of the access sheath/catheter until the removal of the microcatheter;

6. **Robotic Procedure Time** - Defined as the time measured from the first device used robotically until the removal of the microcatheter;
7. **Fluoroscopy Time** - Total fluoroscopy utilized during the procedure as recorded by the Imaging System;
8. **Patient Radiation Exposure** - DAP (dose-area-product) and CD/AK (cumulative dose/air kerma) as recorded during the procedure;
9. **Contrast Volume** - Total contrast used during the procedure;
10. **Adverse Events** - All adverse events (AEs) from the start of the CorPath GRX procedure until the end of the study will be summarized.
11. **Thromboembolic Events** - Defined as rate of thromboembolic events occurring up to 180-days following the robotic-assisted procedure;
12. **Devices Used Robotically** - All devices used will be recorded as successful or unsuccessful in conjunction with the CorPath GRX System;
13. **Aneurysm Occlusion** - Angiographic assessment of aneurysm occlusion grade according to the Raymond-Roy classification scale, parent-vessel compromise, and occlusion durability as assessed from an independent core laboratory. This will be assessed post-procedure and at a 180-day follow-up.

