#### **4.8.6 Specify Device to Be Used Robotically**

After arterial access prior to using the CorPath GRX System, the Investigator will specify which device he/she will plan to use robotically. If a device that is used robotically cannot be delivered to the target, cross the target or delivered into the target and conversion to manual is needed, it will be documented as an unplanned conversion to manual.

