4.4.2 Secondary Endpoint 2: Robotically Navigate Device to the Target Aneurysm

Endpoint: Defined as successful advancement of device TO the target aneurysm robotically. Specifically, success if defined as all guidewires, microcatheters, coils, and stents that may have been used must all have been able to navigate TO the target aneurysm as identified on CRF 9 CorPath GRX Intervention Assessment CRF. Likewise, failure is any single instance where one or more of those listed items were unable to navigate to target lesion.

Subjects to Include: Analysis Cohort

Statistical Analysis: The count and proportion of aneurysms where CorPath was able to navigate TO the target lesion successfully will be calculated along with a 2-sided Clopper Pearson Exact 95% confidence interval.

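### SAP 4.4.2 and 4.4.3 score step endpoints 2 and 3 by an all-devices rule that the protocol does not state, yet report the result as aneurysms reached or entered

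*Protocol*

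**What the plan says.** The protocol words endpoint 2 in two ways. The Study Summary has "Defined as successful advancement of device to the target aneurysm robotically". Section 3.4 has "Defined as successful advancement of devices to the target aneurysm robotically". Endpoint 3 replaces reaching the aneurysm with entering it. None of these texts states an any-or-all rule or a unit of analysis.

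SAP 4.4.2 supplies both. For success, "all guidewires, microcatheters, coils, and stents that may have been used must all have been able to navigate TO the target aneurysm", and "failure is any single instance where one or more of those listed items were unable to navigate to target lesion". The reported statistic is "The count and proportion of aneurysms where CorPath was able to navigate TO the target lesion successfully", with an exact 95% interval. SAP 4.4.3 repeats the same device list and rule for navigation into the aneurysm.

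The primary effectiveness endpoint (protocol 3.2, SAP 4.2) is completion of the robotic procedure "absent any unplanned conversion to manual for guidewire or microcatheter navigation, embolization coil(s) or intracranial stent(s) deployment, or an inability to navigate vessel anatomy". Protocol 4.8.6 takes the case of a robotically used device that cannot get to, across or into the target "and conversion to manual is needed, it will be documented as an unplanned conversion to manual". No section says how a failed device that is replaced without manual conversion is scored.

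**The concern.** The SAP's rule and its label measure different things. The rule asks whether every device tried got there. The label says whether CorPath got to the aneurysm. A reader of the results table will take the second meaning.

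Three consequences follow. An aneurysm that was reached and treated robotically can appear as one CorPath could not reach. The rate depends on how many devices a case used as well as on navigation. In stent-assisted cases, endpoint 3 asks the stent to do something that the protocol's workflow does not ask of it. At stake is the reading of two descriptive endpoints that would naturally be used to see at which step robotic procedures fail.

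**Working it through.** **The plan's own figure.** The step endpoints have no hypothesis, target or power. The effectiveness sample size was reproduced to confirm that it stands apart from this point. With a goal of 80%, an expected 90%, two-sided 95% limits and 80% power, n = ((1.960·√(0.8·0.2) + 0.842·√(0.9·0.1))/0.1)² = 107.4, so 108. By the exact rule, success needs at least 95/108 (lower limit 80.3%), with power 81.0%. Neither calculation uses endpoints 2 or 3.

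**Scoring the same case under each definition**

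| Case | Primary endpoint | SAP 4.4.2 / 4.4.3 |
|---|---|---|
| A device fails and manual conversion is needed | Failure (3.2, 4.8.6) | Failure |
| A device fails, another replaces it and arrives robotically, procedure completed without manual conversion | No unplanned conversion under 4.8.6. Success, unless the vessel-anatomy clause is a separate criterion that the first device met | Failure |
| Stent-assisted coiling completed robotically as in the workflow | Success | Success on 4.4.2; failure on 4.4.3 if read literally |

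The second row is the mismatch from the any-single-failure rule. The third comes from the device list. In the CorPath Use Technique (protocol 4.8.5), step 15 positions the stent across the aneurysm. Protocol 4.8.6 treats crossing the target and delivery into it as different things. SAP 4.4.3 requires all stents used to have navigated into the aneurysm and makes no exception for them.

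**Illustrating the size.** Let q be the chance that a device fails and is replaced without conversion, and k the number of devices used. If devices are independent, the aneurysm is scored a failure with probability 1−(1−q)^k:

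- q=1%, k=4: 1−0.961 = 3.9%
- q=2%, k=6: 1−0.886 = 11.4%
- q=2%, k=12: 1−0.785 = 21.5%
- q=3%, k=10: 1−0.737 = 26.3%

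The documents give neither q nor k, so these are assumed values.

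**On the trial's scale.** Take one aneurysm per subject and 97 primary successes out of 108 (90% of 108 is 97.2; 97/108 = 89.8%). If 10% of those 97 had a replaced device, 9.7 or about 10 of them are step failures and 97−10 = 87 are step successes. The 11 primary failures may pass or fail endpoint 2, since a conversion at deployment can follow successful navigation. The endpoint 2 rate then lies between 87/108 = 80.6% and 98/108 = 90.7%. It can fall below the primary rate but need not.

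**The case against.** A reader might infer that the SAP contradicts the protocol, on the view that the protocol asks only for one device to arrive. The documents do not support that. The Study Summary has no article before the noun, section 3.4 uses the plural, and protocol 6.7 leaves further analysis detail to the SAP. The SAP fills a gap with a prespecified, strict rule, and it is entitled to do so.

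A reader might also infer that every case with a replaced device is a primary success. That too goes beyond the text. The final clause of the primary endpoint, on inability to navigate vessel anatomy, can be read as a failure criterion in its own right. Protocol 4.8.7 also recommends conversion when a device cannot be navigated as intended, so many such cases may fail both endpoints. No section describes a failed device being replaced robotically, and its frequency is unknown. The coil exchange in step 22 is routine.

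The probabilities above also assume independence. Devices in one aneurysm share anatomy and operator, and coils pass through a microcatheter already in place. For a given q, positive dependence would generally lower the figures.

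On stents, protocol 4.8.5 speaks loosely of deploying treatment devices into the aneurysm just after naming coils and stents, so sites may complete the form in that loose sense.

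Finally, endpoint 12 is not a duplicate. It is per device and combines the steps, while endpoints 2 and 3 are per aneurysm and per step.

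These points remove any claim of outright contradiction or known size. They leave the gap between the SAP's rule and its label, the unstated scoring of replaced devices, and the literal stent requirement in 4.4.3. A loose reading of the last by some sites would make the data less consistent.

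**Conclusion.** The point holds as a definitional one. The protocol is silent on any-or-all, and the SAP adds an all-devices rule but labels the result as aneurysms CorPath was able to reach or enter. An aneurysm reached after a replacement without conversion is counted as not reached. Whether it is also a primary success depends on the reading of the vessel-anatomy clause. Read literally, SAP 4.4.3 also fails stent-assisted cases carried out as the protocol describes.

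The size cannot be derived from the documents. The range of 3.9% to 26.3% rests on assumed q, assumed k and independence, and its upper end needs 10 to 12 devices per aneurysm. Endpoints 2 and 3 are descriptive, and the strict rule errs against the device rather than for it. The primary test, N=108 and power do not change.

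**What to change.** - In SAP 4.4.3, limit the rule to the devices meant to enter the aneurysm, and name them so that the SAP and the protocol's workflow agree.
- In SAP 4.4.2 and 4.4.3, report per aneurysm whether it was reached, or entered, under robotic control with no unplanned conversion for that step. Keep the all-devices rate beside it as a labelled row.
- State how a failed device replaced without manual conversion is scored on these endpoints, and whether the vessel-anatomy clause makes it a primary failure.
- Use the same noun and the same any-or-all rule in the protocol's Study Summary and section 3.4.

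The cost is SAP wording and a small protocol clarification. The added rate is less strict, which is why the all-devices rate stays. Before adopting it, confirm that the CRFs record conversion by step. Protocol 4.8.7 mentions only whether a conversion was planned and, if not, why, and the forms themselves are not in the documents.

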### Robotically Navigate Device *into* the Target Aneurysm

Defined as successful navigation of device into the target aneurysm robotically;

### Robotically Deploy Therapeutic Device *into* the Target Aneurysm

Defined as successful deployment of therapeutic device into the target aneurysm robotically;

### Overall Procedure Time

Defined as the time measured from the insertion of the access sheath/catheter until the removal of the microcatheter;

Procedure Title: CorPath GRX Neuro Study Protocol	
Doc Number: 104-08660	
Revision: I	Page: 9 of 69

**Robotic Procedure Time**

Defined as the time measured from the first device used robotically until the removal of the microcatheter;

**Fluoroscopy Time**

Total fluoroscopy utilized during the procedure as recorded by the Imaging System;

**Patient Radiation Exposure**

DAP (dose-area-product) and CD/AK (cumulative dose/air kerma) as recorded during the procedure;

**Contrast Volume**

Total contrast used during the procedure;

**Adverse Events**

All adverse events (AEs) from the start of the CorPath GRX procedure until the end of the study will be summarized;

**Thromboembolic Events**

Defined as rate of thromboembolic events occurring up to 180-days following the robotic-assisted procedure.

**Devices Used Robotically**

All devices used will be recorded as successful or unsuccessful in conjunction with the CorPath GRX System;

**Aneurysm Occlusion**

Angiographic assessment of aneurysm occlusion grade according to the Raymond-Roy classification scale, parent-vessel compromise, and occlusion durability as assessed from an independent core laboratory. This will be assessed post-procedure and at a 180-day follow-up.

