## SCHEDULE OF ACTIVITIES

	Pre-Procedure	Procedure	Post-Procedure	90-day BY PHONE	180-day	Un-Scheduled Visit
		Day (0)	(24-hours post-procedure or hospital discharge)	±14-days	±30-days	
Patient Eligibility Criteria	X					
Submit to Eligibility Committee						

 
• Clinical history
 
• Unruptured Intracranial Aneurysm Treatment Score
 
• Treatment plan
 
• ≥ 4 angiographic (DSA or CTA/MRA) images
 
	X					
Medical History	X 					
Digital Subtraction Angiography (DSA), Computed Tomography Angiography (CTA), or Magnetic Resonance Angiography (MRA)/Magnetic Resonance Imaging (MRI) of the brain/head	X 				X 	
Clinical assessment & Physical exam including:						

 
• Modified Rankin Scale (mRS)
 
• National Institutes of Health Stroke Scale (NIHSS) scale
 
	X		X	X 	X 	X 
Raymond Grade-Roy Occlusion Classification Scale	X 	X			X	
Laboratory Tests: hemoglobin, hematocrit, activated partial thromboplastin time, platelet count, international normalized ratio, pregnancy test, serum creatinine and glomerular filtration rate.	X 		X 			
Procedure Parameters		X				
Catheter Angiography		X 				
Contrast volume		X				
Record of AEs		X	X	X	X	X
Data for aneurysm assessment e.g. tortuosity, proximal & distal vessel diameter, target aneurysm measurements.		X			X	

 Within 7 days of index procedure.

 If performed under standard hospital procedure.

 For previously coiled aneurysms.

 Female subjects of child-bearing potential must have negative pregnancy test (urine or serum).

 Includes angiograms in the anterior posterior, lateral and working positions for analysis by a core laboratory.

 Telephone assessment and mRS is required. Other post procedure clinical assessment (scales/scores/grades) is left to the discretion of the investigator and shall be dictated by the patient's clinical symptoms.

 Post scans will be sent to the core laboratory for analysis.

 mRS is required. Other post procedure clinical assessment (scales/scores/grades) is left to the discretion of the investigator and shall be dictated by the patient's clinical symptoms.

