##### **4.6.1 INCLUSION CRITERIA**

1. Age  $\geq$  18 years.
2. At least one cerebral aneurysm (unruptured) with indication for endovascular treatment; dome to neck ratio  $>1.5$  or aneurysm neck width  $>4.0$  mm.
3. The Investigator deems the procedure appropriate for both manual or robotic-assisted endovascular treatment.
4. The conscious subject has been informed of the nature of the study, agrees to its provisions and has provided written informed consent.

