### 4.8.2 Baseline Date

The following baseline data should be collected for all subjects prior to the planned index procedure (usually routinely done for endovascular robotic procedure subjects with cerebral aneurysms):

- Patient Eligibility Criteria
- Head CT angiography or MR angiography
- Demographics
- Medical history
- Pre-endovascular Patient Assessment conducted by a trained person with appropriate qualifications to perform these evaluations:
  - Modified Rankin score
  - Raymond Grade for previously coiled aneurysms
  - National Institutes of Health Stroke Scale (NIHSS) scale
- Laboratory tests, if performed under standard hospital procedure, *should* be collected for all subjects prior to planned index-procedure (usually routinely done for patients undergoing cerebral aneurysm endovascular procedure \*):
  - Hemoglobin (HGB)
  - Hematocrit (HCT)
  - Activated Partial Thromboplastin Time (aPTT)
  - Platelet count
  - International Normalized Ratio (INR)
  - Pregnancy test
  - Serum creatinine
  - Glomerular Filtration Rate (GFR)

**\* Note:** Pre-endovascular Patient Assessment and laboratory tests must be within 7 days of index procedure. Female patients of child-bearing potential must have a negative pregnancy test (serum or urine).

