#### **11.4 Angiographic Core Lab**

The following assessments will be made by the Angiography Core Lab from images submitted from the sites. The procedural angiograms will be submitted by site with all subject identifiers removed and only the assigned subject study number on the images.

Procedural, pre, peri and post images:

- Aneurysm location
- Raymond-Roy Occlusion Classification grade (pre-procedure required only for previously coiled aneurysms)
- Stenosis of parent and branch arteries(pre-procedure)

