4.1 Definition of Analysis Populations

Analysis Cohort: Any subject with an attempted endovascular procedure (a non-missing robotic microcatheter insertion time).

Per-Protocol Cohort: Any subject in the analysis cohort who did not have a major protocol deviation.

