4.4.13 Secondary Endpoint 13: Aneurysm Occlusion

Endpoints: Angiographic assessment of aneurysm occlusion grade according to the Raymond-Roy classification scale, parent-vessel compromise, and occlusion durability as assessed from an independent core laboratory. This endpoint is assessed post-procedure and at 180-day follow-up.

Subjects to Include: Analysis Cohort

Statistical Analysis: The frequency and proportion of each summary (aneurysm grade, parent-vessel compromise, occlusion durability) along with a 2-sided Clopper Pearson Exact 95% confidence interval will be summarized. Note the confidence interval for summaries of categories with more than 2 categories will be binomial confidence interval for each individual category compared to the rest.

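### SAP 4.4.13 pools never-treated and previously coiled aneurysms and leaves the pre-procedure Raymond-Roy grade unused, so the occlusion table cannot separate a pre-existing remnant from a result of the robotic procedure

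*Protocol*

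**What the plan says.** **Time points.** The protocol (Study Summary and 3.4, no. 13) says of aneurysm occlusion: "This will be assessed post-procedure and at a 180-day follow-up". SAP 4.4.13 agrees: "This endpoint is assessed post-procedure and at 180-day follow-up". Neither names a pre-procedure time point.

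**Analysis.** SAP 4.4.13 reports "The frequency and proportion of each summary (aneurysm grade, parent-vessel compromise, occlusion durability") with exact 95% confidence intervals. It states no hypothesis, no success grade and no performance goal.

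**Population.** The endpoint uses the Analysis Cohort, which SAP 4.1 defines as "Any subject with an attempted endovascular procedure (a non-missing robotic microcatheter insertion time"). Prior coiling plays no part in that definition.

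**Eligibility.** Protocol 4.6.1 asks for "At least one cerebral aneurysm (unruptured) with indication for endovascular treatment", with a size or shape criterion. Nothing in 4.6.1 or 4.6.2 excludes an aneurysm that was coiled before.

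**The pre-procedure grade.** The Schedule of Activities marks the Raymond-Roy row at the pre-procedure visit with the footnote "For previously coiled aneurysms". The baseline list in 4.8.2 includes "Raymond Grade for previously coiled aneurysms". The core-laboratory list in 11.4 includes "Raymond-Roy Occlusion Classification grade (pre-procedure required only for previously coiled aneurysms").

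**The concern.** For a never-treated aneurysm, the grade after the procedure is the anatomical result of that procedure. For a previously coiled aneurysm, the same grade mixes the earlier treatment with the robotic one, and what the robotic procedure did shows only in the change from the pre-procedure grade. The plan arranges to obtain that earlier grade and then gives it no use.

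The trial has a single arm, so no control group absorbs the contribution of earlier treatment. Endpoint 13 is the listed endpoint that describes the angiographic result in the aneurysm; the primary effectiveness endpoint concerns completion without unplanned conversion to manual operation. If the two kinds of aneurysm are mixed in unknown proportion, a reader of the occlusion table cannot say what it measures and cannot correct it from the other planned tables.

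**Working it through.** **Step 1: does any planned analysis use the pre-procedure grade or split by prior coiling?**

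- SAP 4.4.13: one frequency per category in the whole cohort, post-procedure and at 180 days. No change from the pre-procedure grade.
- Protocol 6.3: the only stated split of secondary endpoints is ruptured versus unruptured. Under 4.6.1 the target aneurysm is unruptured, so this split separates nothing relevant here.
- SAP 4.5: a summary of aneurysm characteristics is planned. Prior coiling is not mentioned, and such a summary would not link it to occlusion.
- Occlusion durability is listed in endpoint 13 but not defined in either document, so it cannot be assumed to involve the pre-procedure grade.

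The answer is no.

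**Step 2: direction.** The plan has no figure to reproduce for this endpoint, so the following is illustration. Let m be the number of previously coiled aneurysms whose grade does not change.

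- Unchanged Class II: adds nothing to the Class I count and m to the Class I/II count, with m in both denominators. Class I falls. Class I/II rises slightly, as long as the new-aneurysm rate is below 100%.
- Unchanged Class III: adds nothing to either count. Both rates fall.

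**Step 3: size for Class I (complete occlusion).** Inputs:

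- N = 108, the planned number, taking one aneurysm per subject (assumption).
- m = 5, 11 or 22, about 5, 10 or 20% (assumption; the documents give no share), all unchanged Class II.
- Class I in about 73.6% of new aneurysms. This is borrowed from the 78/106 with complete occlusion and no major stenosis in the published trial shown in protocol Table 5, and is used only for scale.

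Class I count = 0.736 × (108 − m), rounded. Pooled rate = count/108; new-only rate = count/(108 − m).

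| m | Class I count | Pooled | New only |
|---|---|---|---|
| 5 | 76 | 76/108 = 70.4% | 76/103 = 73.8% |
| 11 | 71 | 71/108 = 65.7% | 71/97 = 73.2% |
| 22 | 63 | 63/108 = 58.3% | 63/86 = 73.3% |

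Pooling lowers the rate by about 3 to 15 points.

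**Step 4: size for a combined Class I/II rate.** Assume a pooled result of 92/108 = 85.2%, with all m cases unchanged Class II. Never-treated rate = (92 − m)/(108 − m).

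| m | Never-treated | Pooled minus never-treated |
|---|---|---|
| 5 | 87/103 = 84.5% | 0.7 points |
| 11 | 81/97 = 83.5% | 1.7 points |
| 22 | 70/86 = 81.4% | 3.8 points |

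For comparison, the exact 95% interval for 92/108 is 77.1 to 91.3%.

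**Step 5: unchanged Class III.** Assume about 90% of new aneurysms are Class I/II, that is 93/103, 87/97 or 77/86 (90.3, 89.7 or 89.5%). Adding m unchanged Class III cases to the denominator gives 93/108, 87/108 or 77/108, which is 86.1, 80.6 or 71.3%. The combined rate now falls.

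**The case against.** A reader might infer that the table credits an unchanged remnant to the robotic procedure. The documents do not support that. Endpoint 13 is descriptive and defines no successful grade, and a combined Class I/II outcome appears in neither document. An unchanged remnant is reported as what it is, a residual neck or a residual aneurysm. Protocol 6.7 points 180-day results to the Table 5 layout where appropriate, and there the occlusion measure is complete occlusion, yes or no. An unchanged remnant is a no, which counts against the device. Credit arises only if a reader chooses to treat Class II as adequate.

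A reader might also size the effect as m/108, giving 4.6, 10.2 or 20.4 points. Those figures are the unchanged remnants' share of the pooled table. They keep the cases in the denominator while removing them from the numerator, and so are not the difference between the pooled and never-treated rates. That difference is 0.7 to 3.8 points in Step 4, well inside the sampling interval.

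Other points on this side stand too. The share of previously coiled aneurysms and their class mix are unknown. Having every one unchanged is an extreme case, since each subject needs an indication for treatment and Eligibility Committee approval. Endpoint 4 and the primary effectiveness endpoint also bear on whether devices were deployed. The SAP allows subject listings and plans a summary of aneurysm characteristics, which leaves room for a split without promising one.

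These arguments remove a one-directional reading and a large headline size. They do not make the pooled table interpretable: the mixture remains, and the reading that would resolve it has no stated use.

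**Conclusion.** The point holds as a limited one. The planned Raymond-Roy table cannot separate a pre-existing remnant from a result of the robotic procedure, and pooling can push the figures either way. Under the assumed inputs, the larger error with unchanged Class II remnants is a complete-occlusion rate that looks worse than in new aneurysms (58.3 to 70.4% against about 73 to 74%); the rise in a combined Class I/II rate is at most a few points. With unchanged Class III remnants both rates fall.

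All sizes rest on an assumed number of previously coiled aneurysms, all unchanged, and on assumed rates in new ones, so the true effect could be negligible if few such aneurysms are enrolled. The endpoint is secondary and descriptive: no primary conclusion and no sample size depends on it. It is a worthwhile, inexpensive improvement rather than a threat to the trial's main result.

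**What to change.** In SAP 4.4.13:

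1. Report Raymond-Roy grade overall and separately for never-treated and previously coiled aneurysms, at both planned time points.
2. For previously coiled aneurysms, add a shift table of core-laboratory grade: pre-procedure, post-procedure and 180 days.

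No new visit or image is needed. The core laboratory must already read the pre-procedure grade of these aneurysms (protocol 11.4), and the later readings belong to the endpoint as defined. The site's own pre-procedure grade is only listed among data that should be collected (4.8.2), and no case report form for it is in the documents, so the shift table should use the core-laboratory reading. The cost is SAP wording, one extra table, and smaller denominators with wider intervals in the split rows.
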